7.0 ADVERSE EVENTS

Investigators are responsible for monitoring the safety of patients who have entered this study and for alerting the Cancer Consortium IRB to any event that seems unusual in accordance with IRB policy. The investigator is responsible for the appropriate medical care of patients during the study. The investigator remains responsible to follow, through an appropriate health care option, adverse events that are serious or that caused the patient to discontinue before completing the study. The patient should be followed until the event resolves or stabilizes. Frequency of follow-up is left to the discretion of the investigator.

Safety measurements that will be used in the study include physical examinations and clinical laboratory tests (hematology and blood chemistries). The adverse event will be graded for toxicity using the NCI CTC version 4.0. Toxicity assessment will occur at each visit. Any adverse events leading to a treatment interruption or dose reduction along with all adverse events that are grade 2 or higher related to either study medication, will be recorded.

Before initiation of subsequent cycles, each patient will be evaluated for possible toxicities that may have occurred after the previous treatment. All Grade 3 or 4 toxicities related to study medication should resolve to Grade 1, tolerable, non-clinically significant Grade 2, or baseline before re-initiation of study treatment. Dose modification will be made based on the toxicity with the greatest severity.

7.1 Definition of Dose-Limiting Toxicities (DLT)

A DLT is defined as one of the following adverse events reported during the DLT observation period, if considered to be definitely, probably, or possibly related to either study regimen by the investigator; and fulfills any one of the following criterion using NCI CTCAE Version 4.0:

1. Nonhematologic toxicity as follows:

- a) Grade 4 nonlaboratory toxicity
- b) Grade 3 nonlaboratory toxicity (for example, nausea, vomiting, and diarrhea) lasting >3 days despite optimal supportive care.
- c) Any Grade 3 or Grade 4 laboratory value if:
 - i) Medical intervention is required to treat the patient, or ii)
The abnormality persists for >1 week.

Note: Liver function abnormality: For patients with liver metastasis who begin treatment with Grade 2 aspartate aminotransferase (AST) or alanine amino transferase (ALT), if AST or ALT increases by greater than or equal to 50% relative to baseline and lasts for at least 7 days

2. Hematologic toxicity, as follows:

- a) Grade 4 thrombocytopenia and Grade 4 anemia.
- b) Other grade 4 toxicities lasting ≥ 7 days, or
- c) Grade 3 thrombocytopenia if associated with bleeding and requires platelet transfusion, or
- d) Febrile neutropenia Grade 3 or Grade 4

3. Any grade 5 toxicity

4. Any other significant toxicity deemed by the primary investigator and the sponsor to be dose limiting, for example:

- a) Any toxicity that is possibly related to study treatment that requires the withdrawal of the patient from the study
- b) A delay of > 14 days due to persistent Grade ≥ 2 toxicities in initiating the subsequent cycle, with the exception of Grade 2 fatigue

Any infusion or hypersensitivity reactions occurring during the infusion of the drug are not considered dose-related and therefore will NOT be considered to be a DLT.

Attribution of adverse events.

Unrelated: This relationship suggests that there is no association between the study drug and the reported event.

Unlikely: This relationship suggests that the association between the study drug and the reported event is unlikely.

Possible: This relationship suggests that treatment with the study drug caused or contributed to the AE, ie, the event follows a reasonable temporal

sequence from the time of drug administration or follows a known response pattern to the study drug, but could also have been produced by other factors.

Probable: This relationship suggests that a reasonable temporal sequence of the event with drug administration exists and, based upon the known pharmacological action of the drug, known or previously reported adverse reactions to the drug or class of drugs, or judgment based on the investigator's clinical experience, the association of the event with the study drug seems likely. The event disappears or decreases on cessation or reduction of the dose of study drug.

Definite: This relationship suggests that a definite causal relationship exists between drug administration and the AE, and other conditions (concurrent illness, progression/expression of disease state, or concurrent medication reaction) do not appear to explain the event.

Nivolumab

There will be no dose reductions for nivolumab, dose delays will be discussed below. If an immune related adverse event (irAE) is suspected, a thorough evaluation should be conducted in an effort to rule out neoplastic, infectious, metabolic, toxin or other etiologic causes prior to diagnosing an irAE. Serological, immunological, and histological (biopsy) data should be considered to support the diagnosis of an immune-related toxicity. Systemic corticosteroids (1-2mg/kg/day) are indicated for all grade 3 or grade 4 irAEs if not otherwise specified as below. Steroid should be tapered once symptoms improve to Grade 1 or less and tapered over at least 1 month. Nivolumab should be permanently discontinued for

- Life-threatening or non-hematologic grade 4 toxicity
- Any severe or Grade 3 treatment-related adverse reaction that recurs.
- Inability to reduce corticosteroid dose to ≤ 10 mg of prednisone or equivalent/day within 12 weeks
- Persistent Grade 2 or 3 treatment-related adverse reactions that do not recover to Grade 1 or resolve within 12 weeks after last dose of nivolumab.

Table 1: Dose modification guidelines for toxicities related to Nivolumab

Adverse reaction	Severity	Dose modification*
Pneumonitis	Grade 2	Withhold dose
	Grade 3 or 4	Permanently discontinue
Hepatitis	Aspartate aminotransferase (AST)/or alanine aminotransferase (ALT)	Withhold dose

Clinical Study Protocol 9602
Drug Substance: plinabulin
IND: 129799
Protocol v5.1
Date 7/15/2017

	more than 3 and up to 5 times the upper limit of normal or total bilirubin more than 1.5 and up to 3 times the upper limit of normal	
	AST or ALT more than 5 times the upper limit of normal or total bilirubin more than 3 times the upper limit of normal	Permanently discontinue
Hypophysitis Adrenal Insufficiency Hyperglycemia Rash Colitis or Diarrhea	Grade 2 or 3	Withhold dose
	Grade 4	Permanently discontinue
Nephritis and renal dysfunction	Serum creatinine more than 1.5 and up to 6 times the upper limit of normal	Withhold dose
	Serum creatinine more than 6 times the upper limit of normal	Permanently discontinue
Encephalitis	New-onset moderate or severe neurologic signs or symptoms	Withhold dose
	Immune-mediated encephalitis	Permanently discontinue
Other	Grade 3 first occurrence	Withhold dose
	Recurrence of same grade 3 AE	Permanently discontinue
	Grade 4	Permanently discontinue
* if treatment is withheld, it should be resumed once the adverse events return to grade 0 or 1. If this does not happen in >12 weeks then treatment should be discontinued and the patient should be taken off study		

Patients should receive appropriate supportive care measures as deemed necessary by the treating investigator. Please refer to “Immune mediated adverse reaction management guide” published by Bristol-Myers Squibb for additional recommendations regarding irAE management.

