5.1.3 Phase one

The phase one portion of this trial will be a phase-1 dose escalation to determine the safety of plinabulin in combination with nivolumab. For the initial portion of this phase, 3 patients will be enrolled and will receive plinabulin at a dose of 20 mg/m² as well as nivolumab at 240 mg for 1 cycle. Cycles will consist of plinabulin and nivolumab on days 1 and 15 of a 28 day cycle. After these patients receive at least 1 cycle of treatment, and if no DLTs are seen, another cohort of 3 patients will enroll, and be treated with plinabulin at a dose of 30mg/m² and nivolumab at a dose of 240 mg. If there are no DLTs after the first cycle of treatment, the trial will continue with the second phase of the study. Alternatively, if

one or more patients in either cohort experience a DLT the cohort in question will expand to include a total of 6 patients. If no other DLT are seen in these 6 patients, then the next phase of the study will continue. If two or more (2/6) patients in this cohort experienced a DLT, then will stop and an alternative dose level may be considered after further discussion with the sponsor and analysis of the DLT by the study team. If this were to be the case the protocol will be amended. If a delayed DLT occurs (i.e. a DLT that occurs during cycle 2 of treatment) the DLT evaluation period will be extended to include the first 2 cycles of treatment. For definitions of DLT please see section [7.1](#)

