All subjects who sign consent to participate in this trial will undergo a mandatory biopsy prior to the start of treatment and after 1 cycle of treatment. The biopsy is mandatory but the treating physician must deem the biopsy feasible and safe; if the physician feels that the biopsy is not feasible or it is not safe the subject will still be allowed to enroll in trial. The biopsy will take place at baseline after eligibility criteria has been confirmed and after the first cycle. Tumor tissue samples consisting of core needle biopsies of deep tumor tissue or lymph nodes or excisional, incisional, punch, or forceps biopsies of cutaneous, subcutaneous, or mucosal lesions will be obtained. Fine needle aspirates, cell pellets from effusions or bone biopsies are not permitted. Target lesions considered for core needle biopsies should be deemed suitable for retrieval of at least three cores (minimum diameter 18- gauge). The biopsy will be delivered to the laboratory of [name].

Treatment on Days 1 and 15 of each Cycle.

Cycles are defined as 28 days.

- On Days 1 and 15 of each cycle (+/- 2 days), the following will be performed prior to therapy administration:
 - History and physical examination that includes examination of major organ systems, ECOG performance status (Days 1 only), weight (Days 1 only), vital signs, adverse event evaluation
 - Laboratory evaluations (Days 1 only) including:
 - CBC with differential
 - Serum Chemistry (sodium, potassium, chloride, carbon dioxide, creatinine, BUN, glucose, calcium, albumin, bilirubin, AST, ALT, total protein, and alkaline phosphatase)
 - Thyroid function (TSH, T3, Free T4) will be performed on Day 1 of every ODD cycle

Drug Administration

6.1.1 Dose calculation.

Plinabulin doses will be determined by the patient's actual weight on Day 1 of each cycle, Nivolumab doses are fixed at a flat dose of 240mg.

6.1.2 Schedule of administration.

Patients will receive therapy on days 1 and 15 of a 28 day cycle. Therapy will consist of plinabulin administered via intravenous infusion (IV) over 30 minutes (+/- 5 minutes) followed by nivolumab administered via intravenous infusion (IV) over 60 minutes (+/- 10 minutes).

- Cycles one and two require a 1-hr observation period between plinabulin and nivolumab administration. No observation period will be required in subsequent cycles if infusions were tolerated without any infusion reactions.

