Patients who discontinue treatment without receiving study medication will be replaced. No other patients will be replaced

Clinical Study Protocol 9602
Drug Substance: plinabulin
IND: 129799
Protocol v5.1
Date 7/15/2017

Schedule of events

	Screening ¹	Cycle 1		Cycle 2+		Off Study ¹²	Survival follow up
		Day 1 +/- 2 days	Day 15 +/- 2 days	Day 1 +/- 2 days	Day 15 +/- 2 days		
Informed consent ²	X						
Demographics	X						
Medical history	X						
Concurrent meds	X	X	X	X	X	X	
Physical exam	X	X	X	X	X	X	
Adverse event evaluation		X	X	X	X	X	X ¹³
Vital signs ³	X	X ¹⁴	X ¹⁴	X ¹⁴	X ¹⁴	X	
Height, weight ⁴	X	X		X		X	
Performance status	X	X		X		X	
Biopsy ⁵	X			X			
CBC w/differential	X	X		X		X	
Serum chemistry ⁶	X	X		X		X	
Thyroid Function ⁷	X	X		X ⁷			
Serum pregnancy test	X ⁸						
Disease assessment (CT scan) ⁹	X			8 (±1) weeks, starting in C7 12 (±1) weeks ¹⁰		X	
Brain CT or MRI	X ¹¹	As clinically indicated					
Survival assessment							X
Plinabulin		X	X	X	X		
Nivolumab		X	X	X	X		

1: screening evaluations must be performed within 28 days of Cycle 1 Day 1
2: consent must be performed prior to initiation of any screening or study-specific procedures

Clinical Study Protocol 9602
Drug Substance: plinabulin
IND: 129799
Protocol v5.1
Date 7/15/2017

- 3: vital signs should include: temperature, blood pressure, heart rate, and respiratory rate
- 4: height is needed at screening only
- 5: biopsy is mandatory for all subjects if treating physician deems it to be safe and feasible. If treating physician deems biopsy not safe and/or not feasible the subject may still be enrolled if they meet all other inclusion criteria.
- 6: sodium, potassium, chloride, carbon dioxide, creatinine, BUN, glucose, calcium, albumin, total bilirubin, AST, ALT, total protein, and alkaline phosphatase
- 7: TSH, T3, Free T4 will be performed at screening and Day 1 of every ODD cycle
- 8: serum pregnancy test (for women of childbearing potential only). Subjects must use an acceptable method of birth control.
- 9: CT scan scan of known sites of involvement. A prior CT scan that is no more than 28 days before the initiation of treatment may be used.
- 10: disease will be assessed 8 (\pm 1) weeks, after cycle 7 patients will be reimaged every 12 (\pm 1) weeks.
- 11: brain CT or MRI does not need to be repeated if scans were performed within 28 days of C1D1
- 12: off-study evaluation will be performed within 28 days (\pm 7 days) after last dose of study treatment

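### No post-dose laboratory draw is scheduled in cycle 1 before Cycle 2 Day 1, so DLT criteria needing about 7 days of abnormality cannot be documented from scheduled draws in the cycle that decides escalation

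*Combined protocol and SAP*

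**What the plan says.** Section 5.1.3 bases escalation and the move to phase 2 on DLTs in the first 28-day cycle, in cohorts of 3 or 6: "If there are no DLTs after the first cycle of treatment, the trial will continue with the second phase of the study".

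Section 7.1 makes three DLT items depend on how long a laboratory or blood-count abnormality lasts:
- item 1c(ii), for a Grade 3 or 4 laboratory value: "The abnormality persists for >1 week"
- item 2b, hematologic: "Other grade 4 toxicities lasting ≥ 7 days"
- the liver note, for patients with liver metastasis who start at Grade 2 AST or ALT: "if AST or ALT increases by greater than or equal to 50% relative to baseline and lasts for at least 7 days"

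Item 1c(i) is the alternative to 1c(ii) and has no duration: "Medical intervention is required to treat the patient". Item 2a, Grade 4 thrombocytopenia or anemia, has none either.

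Section 6 (Treatment on Days 1 and 15 of each Cycle) lists what is done at the two dosing visits: "the following will be performed prior to therapy administration". Within that list the blood tests are restricted: "Laboratory evaluations (Days 1 only) including". The Schedule of events agrees. The row "CBC w/differential" and the serum chemistry row, which includes AST, ALT, total bilirubin and creatinine, are marked at screening, Cycle 1 Day 1, Day 1 of later cycles and the off-study visit. Both are blank on Day 15.

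**The concern.** The DLT definition asks for information that the visit schedule does not collect. The only scheduled laboratory draw at a cycle 1 treatment visit is the pre-dose baseline. Any value that shows an effect of the drugs comes at Cycle 2 Day 1, when the deciding cycle is over. Following the plan exactly, the team has no second abnormal value with which to show persistence. A Grade 4 thrombocytopenia or anemia that causes no symptoms and recovers before Cycle 2 Day 1 would not be seen, although item 2a needs no duration.

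Two things are at stake. First, unmeasured events can only lower the DLT count, and one event matters in a cohort of 3 or 6. Second, the dosing rules act on values that are not scheduled before the Day 15 dose. Table 1 withholds nivolumab for AST or ALT above 3 x ULN, bilirubin above 1.5 x ULN or creatinine above 1.5 x ULN. Section 7.4 stops plinabulin permanently for AST or ALT above 3 x ULN together with bilirubin above 2 x ULN.

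**Working it through.** The plan states no figure on this point to reproduce, and gives no laboratory DLT rate and no episode durations. The check is therefore a count of draws, followed by an illustration under stated assumptions.

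**Inputs from the protocol.** 28-day cycle with both drugs on Days 1 and 15 (5.1.3, 6.1.2); visits within +/- 2 days, and CBC and chemistry pre-dose on Day 1 only (section 6, Schedule of events); decision after cycle 1 (5.1.3); persistence of about 7 days (7.1).

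**Assumed.** Onset is uniform between the first dose and Cycle 2 Day 1, and an episode lasts d = 8, 14, 21 or 28 days. Time runs in days from the first dose: Day 15 is at t1 = 14 (window 12 to 16) and Cycle 2 Day 1 is at t2 = 28 (window 26 to 30).

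**Step 1: count.** Scheduled post-dose draws before Cycle 2 Day 1: 0. Scheduled AST/ALT, bilirubin or creatinine values between the first and second doses: 0. One draw at t2 can show that an abnormality is present, but not that it has lasted 7 days. The next scheduled draw is Cycle 3 Day 1, another 28 days later. The share of episodes whose persistence is documented within cycle 1 is therefore 0% for every d.

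**Step 2: share of episodes never seen.** An episode is missed if it starts and ends between draws.
- Cycle 2 Day 1 only: max(0, t2 - d) / t2
- Day 15 added: [max(0, t1 - d) + max(0, t2 - t1 - d)] / t2

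| d (days) | Cycle 2 Day 1 only | Day 15 added |
|---|---|---|
| 8 | 20/28 = 71% (69-73%) | (6 + 6)/28 = 43% (38-47%) |
| 14 | 14/28 = 50% (46-53%) | 0/28 = 0% (0-13%) |
| 21 | 7/28 = 25% (19-30%) | 0% (0%) |

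Brackets give the range over the visit windows. For example, 18/26 = 69% and 22/30 = 73% for 8 days; with t1 = 12 and t2 = 30, 14-day episodes give (0 + 4)/30 = 13%.

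**Step 3: share that can be timed within cycle 1.** Suppose an abnormal value is repeated. After an abnormal Day 15 draw, at least 7 further days remain if onset lies between max(0, t1 + 7 - d) and t1. The share is min(d - 7, 14)/28:
- d = 8: 1/28 = 4%
- d = 14: 7/28 = 25%
- d = 21: 14/28 = 50%
- d = 28: 14/28 = 50%

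Today all four are 0%. Episodes that start after Day 15 first show at Cycle 2 Day 1, and any timing of them falls in cycle 2.

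**Step 4: dependence on onset.** With Cycle 2 Day 1 alone, an 8-day episode is missed if it starts before t = 28 - 8 = 20. With Day 15 added, it is missed if it starts at t = 0 to 6 or 14 to 20, that is, within 6 days after a dose. If onsets cluster there, Day 15 gains nothing for such short episodes. If they cluster at t = 6 to 14, Cycle 2 Day 1 alone misses all of them and Day 15 sees all of them. With draws on time, an episode of 14 days or more is always seen once Day 15 is added, wherever it starts.

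**The case against.** The plan has real backstops.
- Unscheduled tests are not barred. Section 7.0 names laboratory tests among its safety measurements and has toxicity assessed at every visit. History, examination and adverse event review precede the Day 15 dose.
- A measured Grade 3 or 4 laboratory value that needs treatment is a DLT at once under 1c(i). The nivolumab guidance in section 7 calls for systemic steroids for Grade 3 or 4 immune-related events unless otherwise specified, so many measured liver events would count without any timing.
- Item 4b offers a delay of more than 14 days as a further ground for a DLT.
- A value still abnormal at Cycle 2 Day 1 can be followed, and section 5.1.3 extends the DLT period if a DLT occurs in cycle 2.
- Section 7.4 reports no severe hematological toxicity with single-agent plinabulin, and 30 mg/m² was already its recommended dose and was used with docetaxel.

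Most of this stands, and it narrows the point. A reader might infer that the Day 15 dose is given with no liver values at all; the documents support only that none is scheduled. None of the backstops reaches a value that was never measured, however. No rule requires a repeat, and nothing in 5.1.3 makes the next cohort wait for one. Experience with plinabulin alone or with docetaxel does not settle liver safety with nivolumab, which is what phase 1 is meant to test.

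**Conclusion.** The point holds for scheduled draws. Section 6 and the Schedule of events agree, so the duration-based laboratory DLTs cannot be documented from them within cycle 1. What remains after the backstops is a silent, untreated episode that resolves before Cycle 2 Day 1, plus a Day 15 dose that may be given without a scheduled value for the thresholds in Table 1 and section 7.4.

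The percentages in the working rest on uniform onset and on assumed durations, neither of which the documents supply; they illustrate the size of the gap and do not estimate an event rate.

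Two stronger readings are not supported. A reader might infer that cohorts pass too easily by some calculable amount; without a laboratory DLT rate, no effect on cohort decisions can be claimed. A reader might also credit a Day 15 draw with timing min(1, (d - 7)/14) = 7%, 50%, 100% and 100% of 8-, 14-, 21- and 28-day episodes. That counts persistence measured in cycle 2, after the next cohort may have opened; the within-cycle shares are 4%, 25%, 50% and 50%. The change should be made because it is cheap and bears on both safety and the DLT count.

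**What to change.** 1. In section 6 and the Schedule of events, add for phase 1: *CBC with differential and serum chemistry are also drawn before dosing on Cycle 1 Day 15, and the results are reviewed before the dose is given.*
2. Add: *In phase 1, any Grade 3 or 4 laboratory value, or an AST or ALT rise of 50% or more from a Grade 2 baseline, is repeated about 7 to 8 days later, or sooner at the investigator's discretion. The escalation decision waits for any pending repeat.*
3. For cohorts already completed, report the laboratory values available between Day 1 and Cycle 2 Day 1. Where there are none, state that duration-based laboratory DLTs were not assessable.

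The cost is one extra draw per phase 1 patient at an existing infusion visit (2 cohorts x 3 to 6 patients = 6 to 12 draws if both cohorts open), a short wait for results on Day 15, and a few repeat draws, some of which may fall between infusion visits.

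The change does not close the whole gap. Short episodes that begin soon after a dose can still be missed, and Day 15 doses in later cycles and in phase 2 stay without a scheduled value. Draws on Days 8 and 22 would see every episode of 7 days or more if taken on time, but they need new visits (2 x 6 to 12 = 12 to 24), so they are optional. The liver note in 7.1 is an unfinished sentence; that is a separate drafting point.

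### Sections 5.1.3 and 7.1 do not agree on when a DLT can be counted, or on whether a fatal infusion reaction is one, so a cohort can be cleared before a listed DLT is observable

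*Combined protocol and SAP*

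**What the plan says.** **Decision timing (5.1.3).** For the first cohort: "After these patients receive at least 1 cycle of treatment, and if no DLTs are seen, another cohort of 3 patients will enroll". For the second: "If there are no DLTs after the first cycle of treatment, the trial will continue with the second phase of the study". A cohort with a DLT expands to 6 patients. It passes if there is no further DLT, and the trial stops for discussion if there are 2 or more in 6.

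**Extension (5.1.3).** If a DLT occurs during cycle 2, "the DLT evaluation period will be extended to include the first 2 cycles of treatment".

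**DLT definition (7.1).** A DLT is "one of the following adverse events reported during the DLT observation period" that is at least possibly related and meets a listed criterion. Section 7.1 gives no length for that period. Item 4 covers other toxicities that the investigator and sponsor judge dose limiting. Its example 4b is "A delay of > 14 days due to persistent Grade" 2 or higher toxicity (Grade 2 fatigue excepted) in starting the next cycle.

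**Fatal events (7.1).** Item 3 makes any Grade 5 toxicity a DLT and states no exception. The closing sentence says that infusion or hypersensitivity reactions during the infusion are not dose-related "and therefore will NOT be considered to be a DLT". It sets no grade limit.

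**The concern.** The only observation period that can be read from 5.1.3 is cycle 1, because both decisions are allowed at its end. A criterion that needs more than 14 days' delay to the next cycle cannot be met by then. The extension clause looks like the remedy, but it is triggered by an event outside the original period and does not hold the decision while that event is awaited. On fatal infusion reactions, two statements in the same section point in opposite directions and no order of precedence is given.

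The rule turns on single patients: 0/3 passes and 1/3 expands; 1/6 passes and 2/6 stops. One event that is missed, or counted only later, can change the decision. The dose that passes is the one used in the Simon design of 33 patients in 9.1.

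**Working it through.** The documents state no operating characteristics for the DLT rule, so there is no figure of the plan's own to reproduce. The check is day arithmetic, a reading of the clauses, and one illustration.

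**1. When 4b can first be met**
- Cycle length (section 6.0, treatment days): "Cycles are defined as 28 days". Cycle 1 ends on Day 28 and cycle 2 is due on Day 29.
- A delay of more than 14 days means at least 15: 29 + 15 = Day 44.
- The dosing-day window is ±2 days, so cycle 2 may fall due on Day 27 to 31: 27 + 15 = Day 42 and 31 + 15 = Day 46.
- Gap from the end of cycle 1: 44 − 28 = 16 days.

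**2. Whether the extension closes the gap**
- Trigger: a DLT during cycle 2. If cycle 2 means treatment actually begun, a patient still on hold has not entered it and the clause does not apply. If it means calendar Days 29 to 56, Day 44 is inside.
- Circularity: 7.1 requires the event to be reported within the observation period, but the period lengthens only after a DLT has occurred beyond it.
- Timing: on either reading, nothing in 5.1.3 delays escalation or the opening of the second phase until the longer period has passed.
- Consequence: a late DLT can feed the expand-or-stop rule for the cohort in question, but the text does not say what happens to patients already enrolled at the next step.

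**3. A fatal reaction during infusion**
- Under item 3, it is a DLT.
- Under the closing sentence, it is not.
- If the closing sentence is a carve-out from the whole list, the death does not count towards the dose decision. If it is not a carve-out, the two statements conflict.

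**4. Illustration (all rates assumed)**

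Let q be the probability that a patient has a counted DLT. A cohort passes with 0/3, or with 1/3 followed by 0/3:

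P(clear) = (1 − q)³ + 3q(1 − q)² × (1 − q)³ = (1 − q)³ + 3q(1 − q)⁵

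| In-window DLT | Delay-only DLT, counted | q | Calculation | P(clear) |
|---|---|---|---|---|
| 15% | 0% | 0.15 | 0.6141 + 0.1997 | 0.81 |
| 15% | 5% | 0.20 | 0.5120 + 0.1966 | 0.71 |
| 15% | 10% | 0.25 | 0.4219 + 0.1780 | 0.60 |

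The first row also describes the case where delay-only events occur but cannot count. The gap is therefore 0.10 with a 5% delay-only rate and 0.21 with 10%.

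**The case against.** Several points on the other side are sound.

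- **4b is not automatic.** It is an example under a discretionary item, so a reader who infers that every such delay is a DLT that the plan fails to count goes beyond the text. What stands against the plan is that the judgement cannot be made at the end of cycle 1 about a delay that has not yet run.
- **The wording allows later counting.** Section 7.1 can be read to require only that the toxicity be reported in the period, with the criterion fulfilled afterwards. Cycle 2 can also be read as calendar time. On those readings the event is counted, though possibly after the dose has been cleared. It would be wrong to say that the extension can never help. Nor does 5.1.3 set a Day 28 deadline: for the first cohort it sets a minimum of one cycle.
- **Delay-only events may be uncommon.** Items 1b, 1c, 2a and 2b already capture most lasting Grade 3 and Grade 4 events, so what is left is mainly persistent Grade 2 toxicity. Against this, the nivolumab modification table withholds treatment for Grade 2 pneumonitis and Grade 2 colitis until Grade 0 or 1 and allows up to 12 weeks, so long delays are foreseen.
- **The infusion exclusion is limited and may be deliberate.** It covers reactions during the infusion only and gives a reason. A specific carve-out from a general list is an ordinary reading. A death would still be reported as an SAE within 24 hours under 8.2, and 8.3 provides for DSMC oversight. It would therefore not go unseen, but on this reading it would not count as a DLT.

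**Conclusion.** The mismatch is real but narrower than it may first appear. As written, a cohort can be cleared about 16 days before example 4b can be met, and the extension clause neither clearly covers a patient whose cycle 2 is on hold nor holds the decision. A fatal reaction during infusion has two answers, or is uncounted if the exclusion is a carve-out.

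A reader might infer that the plan is certain to miss qualifying toxicities, or that 0.81 versus 0.60 estimates the error. The documents support neither. The first depends on how 7.1 and the extension are read. The second rests on assumed rates of 15% and 10%, and on every delay-only event being judged a DLT; a lower delay-only rate gives a smaller gap. Nor should the 33 patients in 9.1 all be taken as additional: 9.1 and 9.2 count patients treated at 30 mg/m² or the MTD, which may include phase 1 patients.

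The remaining ambiguity can change a dose decision that rests on 3 to 6 patients, and it can be removed by wording. It should be corrected.

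**What to change.** Reconcile 5.1.3 and 7.1 on three points:

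1. State the length of the DLT observation period in 7.1, and make it, the timing of the cohort decision in 5.1.3 and the delay criterion in 4b agree. Include whether a patient whose cycle 2 has not started falls under the extension.
2. State how a DLT in cycle 2 affects enrolment already open in the next cohort or the second phase.
3. State which prevails for a fatal reaction during infusion: the Grade 5 criterion or the exclusion.

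The content of each rule is for the clinical team. The cost is protocol wording and, depending on what is chosen, possibly a short wait before a cohort decision when a patient's cycle 2 is delayed.
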